6. DETERMINATION OF PROTOCOL DEVIATIONS

6.1 Definition of Protocol Deviations

The CSR-reportable PDs are defined in accordance with ICH E3 as important PDs related to study inclusion or exclusion criteria, conduct of the trial, subject management or subject assessment resulting in the potential to jeopardize the safety or rights of the trial subjects or the scientific value of the trial. Protocol deviations will be classified as CSR-reportable and non-CSR-reportable.

The Protocol Deviation Specification Document for this study lists all the pre-specified observable and programmable PDs, including their classification, categories, subcategories and impact on the analysis.

CSR-reportable PDs may lead to exclusion of the subject or part of the subject's data from at least the PPS.

The number of subjects with any major PD and by PD category and subcategory will be summarized by study treatment and overall. Individual subject listings of major PD will be provided sorted by study treatment, subject, visit and date.

6.2 Determination of Protocol Deviations

The source/method of identification can be either observable or programmable. Programmable PDs are those which can be programmed from the data recorded in the clinical database. Depending on the type of PD, this can be done directly in the database using edit checks. Or separate offline PD listings are created, which are reviewed manually and will lead to triggering PDs in the clinical database. Observable PDs are those that can only be identified by Clinical Research Associates during monitoring or by other team members and are recorded in Impact Harmony.

All PDs will be collected according to the Protocol Deviation Specification document in a web-based protocol deviation tool. The protocol deviation tool and process are overseen by Data Management. Extracts from the tool will be provided regularly for review. Categorization of PDs as major / minor and potential exclusion of the subject from an analysis set will be captured as agreed during the review in the PD tool.

Prior to database lock and unblinding, all PDs will have been reviewed and categorized. A Blinded Data Review Meeting will take place to discuss and confirm assignment of subjects to analysis sets based on the final protocol deviations. Blinded Data Review Meeting minutes and analysis sets will be signed off by at least the Biostatistician and the Clinical Scientist prior to unblinding.

Classification of protocol deviations (and associated actions for analysis sets) that can only be assessed after unblinding, e.g. administration of study drug from the wrong treatment arm, will be

discussed as much as possible before unblinding considering all potential scenarios. However, the final assessment can only be confirmed based on the unblinded locked database. Therefore, final classification of such PDs will be carried out after unblinding. Documentation will be signed off again by at least the Biostatistician and the Clinical Scientist.

6.3 Exclusions of Individual Values for Safety Analysis

Solicited local and systemic AEs will be directly measured and reported by the subject in the eDiary and will not be subject to a reconciliation process, even if they are biologically implausible.

Therefore, these implausible measurements will be removed and counted as missing in the analysis but included in listings. Implausible measurements are summarized in the table below.

Table 4 **Implausible Solicited Adverse Events**

Parameter	Implausible measurements
Body temperature	$\leq 33^{\circ}\text{C}$ or $\geq 42^{\circ}\text{C}$
Erythema	≥ 900 mm or <0 mm
Induration	≥ 500 mm or <0 mm
Ecchymosis	≥ 500 mm or <0 mm

7. ANALYSIS SET

7.1 All-Enrolled Set

All screened subjects who provide informed consent, received a subject ID, and provide demographic and/or baseline screening assessments, regardless of the subject's randomization and treatment status in the study.

Demography and baseline characteristics tables as well as subject listings will be produced on the All-Enrolled Set. Subjects will be analyzed according to the randomized treatment.

7.2 All-Exposed Set

All subjects in the All-Enrolled Set who received a study vaccination. Subjects will be analyzed according to the actual treatment received.

7.3 Full Analysis Set (FAS), Immunogenicity

All subjects in the All-Enrolled Set who are randomized, received study vaccination and provide immunogenicity data at any time point.

In case of vaccination error, subjects in the FAS sets will be analyzed "as-randomized" (i.e., according to the vaccine the subject was designated to receive, which may be different from the vaccine the subject actually received).

See [section 4.1.1](#) for details on how to handle subjects randomized in the wrong stratum.

The FAS Immunogenicity will be used for immunogenicity superiority comparisons on Day 22 and for evaluation of immune response persistence. FAS Immunogenicity will also be used for sensitivity analysis for PPS Immunogenicity based primary non-inferiority analyses.

7.4 Per Protocol Set (PPS), Immunogenicity

All subjects in the FAS Immunogenicity who:

- Have both Day 1 and Day 22 immunogenicity assessment.
- Correctly receive the vaccine (i.e., receive the vaccine to which the subjects are randomized and at the scheduled time points).
- Have no protocol deviations leading to exclusion (see [section 6](#), Determination of Protocol Deviations) as defined prior to unblinding / analysis.

In case of randomization error, if a subject receives a vaccine kit, labelled for another subject but containing the same vaccine as the one the subject was randomized to, the subject will not be removed from the PPS.

In case of vaccination error, the subject is excluded from the PPS.

See [section 4.1.1](#) for details on how to handle subjects randomized in the wrong stratum.

If a subject is unblinded during the study (except for possible SUSARs), he/she will be excluded from the PPS (see also [section 4.2](#)).

The PPS Immunogenicity will be used for noninferiority comparisons and exploratory analyses. PPS Immunogenicity will also be used for sensitivity analysis for FAS immunogenicity analysis where is applicable. Immunogenicity blood samples on Day 181 or 271 qualified to be excluded by protocol deviation review will not be included in Day 181 or Day 271 immunogenicity analyses.

7.5 Safety Set

Solicited Safety Set

All subjects in the All-Exposed Set with any solicited AE data including temperature measurements or use of analgesics/antipyretics.

All solicited safety analyses will be performed based on the Solicited Safety Set.

Unsolicited Safety Set (unsolicited adverse events)

All subjects in the All-Exposed Set who provided unsolicited AE data. Subjects are excluded when they have a confirmed PD of the following category “Subject did not provide or was not available for unsolicited post-vaccination safety assessment at all”.

All unsolicited safety analyses will be performed based on the Unsolicited Safety Set.

Overall Safety Set

All subjects who are in the Solicited Safety Set or Unsolicited Safety Set.

In case of randomization error, subjects will be analyzed as “treated” (i.e., according to the vaccine a subject receives, rather than the vaccine to which the subject is randomized) in all safety sets.

In case a subject is randomized in the wrong stratum:

- Subject will be analyzed in their actual subgroup for all safety analyses.

If a subject is unblinded during the study, he/she will be included in all the safety analyses.

7.6 Other Analysis Set

Not applicable

8. GENERAL ISSUES FOR STATISTICAL ANALYSES

All EDC data up to Visit 6 (Day 271) at the time of database lock, immunogenicity serum lab samples supporting primary and secondary objectives collected up to Visit 5 (Day 181) and protocol deviations (except for Day 271 serum sample analysis PDs) will be used to support final CSR analysis.

For the exploratory objective of persistence of the immune response at 9 months after vaccination, HI antibody responses for all strains included in the study vaccines will be evaluated using an egg-derived target virus at a later stage. For this analysis, Day 1 serum samples obtained for the primary and secondary study objectives (noninferiority, superiority assessments at Day 22 and persistence at Day 181) will be retested together with the Day 271 sample. Day 1 data from the exploratory assessment of persistence at 9 months (retested result) will not replace data obtained for the primary and secondary endpoint analyses. Similarly, if there is insufficient Day 1 serum sample for retesting, the original Day 1 result will not be imputed in the exploratory analysis of persistence at Day 271 in the CSR addendum. and results have been transferred and will be reported in a CSR addendum.

8.1 Adjustment for Covariates

The main statistical analysis includes descriptive statistics for the overall population. Subgroup analyses will be done by age cohort (50-59 and 60-64 year of age), previous vaccination history, sex, race, ethnicity, and comorbidity risk scores (Hak score, <50 and ≥ 50). Summary tables will show unadjusted GMTs for each vaccine group by time point.

Adjusted GMTs will be calculated based on the \log_{10} -transformed antibody titers at Day 22/181/271 using an ANCOVA model which includes the vaccine group (aQIV and QIV), \log_{10} -transformed pre-vaccination antibody titer, age cohort (50-59 or 60-64 year of age), sex, and history of any influenza vaccination within the 3 previous seasons (yes/no). The main analysis of binary immunogenicity endpoints (i.e., percentages of subjects with seroconversion) will not be adjusted for any of the covariates. Binary data will be summarized for each group using unadjusted estimates and will be reported together with two-sided 95% CIs calculated according to the Clopper-Pearson method. Sensitivity analysis may be done to include the vaccine group (aQIV and QIV), stratification factors age and previous vaccination history, and sex in a generalized linear model

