8.3.7 Subgroup(s)

Primary and secondary analyses of immunogenicity and safety endpoints will be done for the total population and by age subgroup (50-59 and 60-64 years of age).

Additional subgroup analysis will be conducted by:

- previous vaccination history
- sex
- race
- ethnicity
- comorbidity risk score (<50 and ≥50)

Refer to the SAP for further details.

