8.4.2.3.3 Statistical Methods

All statistical analyses for HI (or MN if applicable) titers will be performed on the logarithmically (base 10) transformed values. Individual HI titers below the detection limit (<10) will be set to half of that limit (5); values above the upper limit of quantification will be set to the upper limit.

Reverse cumulative distribution curves will be derived by time-point and strain.

Crude estimates for GMTs, GMFIs, and pertaining 2-sided 95% CIs will be calculated assuming a log-normal distribution of the titers and will be completed by providing minimum, maximum and median titers for each treatment group. Binary data (i.e., percentages of subjects with seroconversion and with titer $\geq 1:40$) will be summarized for each group using crude estimates and will be reported together with 2-sided 95% CIs calculated according to Clopper's and Pearson's method ([Clopper and Pearson 1934](#)). No multiplicity adjustment to the CI levels will be implemented.

The analysis model for the HI GMT will use a general linear model on log-transformed (base 10) Day 22 titers as the outcome variable and as covariates: treatment groups (aQIV, and QIV), prevaccination titer (\log_{10} transformed), age stratum, gender, and history of any influenza vaccination within the 3 previous influenza seasons. From this model, adjusted differences in the least square means (on the \log_{10} scale) will be produced with 95% confidence limits for QIV versus aQIV. The estimated difference and the confidence limits will be back-transformed to obtain *adjusted GMT ratios* with 95% confidence limits. The adjusted GMT ratio will be the result for which the assessment of the HI GMT primary endpoint will be based on. Each of the 4 strains will be analyzed separately.

Potential covariate interaction effects will also be examined in the fit of the GLM, as well as the other co-variates such as age taken as a continuous factor.

The differences of binary endpoints (i.e. seroconversion or titer $\geq 1:40$) will be compared using the Miettinen and Nurminen method ([Miettinen and Nurminen 1985](#)). Additional supportive analyses might be done using generalized linear models with factors for treatment group, age subgroup, prevaccination titer (\log_{10} transformed) as well as vaccination history. Adjusted differences between treatment groups with 2-sided 95% CI will be calculated based on the model and potential interaction effects will be examined.

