4. RANDOMIZATION AND BLINDING

4.1 Method of Group Assignment and Randomization

Enrolled subjects will be assigned a subject ID and randomized in the IRT system in a 1:1 ratio to receive either aQIV or QIV with age group (50 to 59, and 60 to 64 years of age), and history of any influenza vaccination within 3 previous influenza seasons (yes/no) as stratification factors. Approximately 50% of subjects will be enrolled into each age group. The Subject ID will be the subject's unique identification number for all eCRFs and associated study documentation that will be used for duration of the study. After randomization, the Screening Number ceases to be used and remains in the Screening and Enrolment Log only. The list of randomization assignments is produced by the IRT service provider and approved by Seqirus according to applicable Seqirus Standard Operating Procedure (SOP).

If for any reason, after signing the informed consent form (ICF), the subject who is eligible and enrolled fails to be randomized, this is called a randomization failure and the early termination study procedures must be applied. The reason for all randomization failures should be recorded in the Screening and Enrolment Log and in the source document. The information on subjects who are randomization failures should be kept distinct from subjects who are screen failures, as described in protocol section 5.1.2, Screening.

If for any reason, after randomization the subject fails to undergo treatment or the subject has discontinued, the reason should be recorded in source document and in the eCRF. The information on discontinued subjects should be kept distinct in the source documentation from randomization failures.

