4.1.1 Definition of Randomization/Vaccination Errors

The list below provides categories for errors that may occur during randomization and/or vaccination.

Randomization errors:

- Administered wrong kit (Subject received vaccine from a kit different from the kit number that was assigned at randomization).

Vaccination errors:

- Administered only part of the study vaccine.
- Incorrect vaccine administration (e.g. incorrect location or route)
- Administered expired vaccine.
- Administered temperature deviated vaccine.

Stratification error:

- Subject randomized in the wrong stratification stratum.

Differentiate between incorrect stratification and randomization errors.

A randomization error is defined as a subject receiving a vaccine from another kit than the one assigned by randomization. If after unblinding, it appears that the vaccine from the incorrect kit is identical to the vaccine from the assigned kit, the error will be reported as a major protocol deviation (PD), but the data from the subject will not be excluded from any analyses sets. If the vaccine is different from the vaccine in the assigned kit, the randomization error is a Clinical Study Report (CSR) - reportable PD and the subject's data should be analyzed as randomized in Full Analysis Set (FAS), excluded from Per Protocol Set (PPS) and analyzed as received for Safety.

Incorrect stratification is defined as enrollment and randomization of a subject based on incorrect stratification information at baseline. Incorrect stratifications should be split for major and minor errors.

- Major stratification errors are those resulting in administration of incorrect dosage or schedule, not corrected on time, i.e. not corrected before administration of the vaccine. These will be handled as CSR-reportable PD.
- Minor stratification errors are those not having impact on dose/schedule administered. These will not be considered as CSR reportable PD.

Since the vaccine dosage and regimen in this study are independent from the stratification factors, major stratification errors are not applicable. In the analysis of covariance (ANCOVA) and in the subgroup analyses, subjects will be analyzed according to their actual age and/or influenza vaccination history.

Stratification error	FAS	PPS	Safety Sets All-Enrolled Set All-Exposed Set
Minor	Analyze as corrected	Analyze as corrected	Analyze as corrected
Major*	Analyze as originally stratified	Exclude from analysis	Analyze as corrected

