8.5 Subgroups

Adjusted (same model as the main analysis by subgroup with subgroup factor removed if it is in the main model) and unadjusted immunogenicity analysis of the GMTs and SCRs will be performed by stratifying for the following subgroups:

- Age cohort (50-59 and 60-64 years of age)
- Previous vaccination history (Yes and No)
- Sex
- Race
- Ethnicity
- Comorbidity risk score (<50 and ≥ 50)

Safety analysis will be performed by stratifying for the following subgroups:

- Age cohort (50-59 and 60-64 years of age)
- Previous vaccination history (Yes and No)
- Sex
- Race
- Ethnicity
- Comorbidity risk score (<50 and ≥ 50)

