$$\mu_{ijlmkn} = \lambda_k + \eta_{ik} + \alpha_{jk} + \gamma_{lk} + \xi_{mk} + \beta \tau_{0ik} + \varepsilon_{ijlmkn} \quad (k=1, 2, 3, 4 \text{ strains})$$

where $\varepsilon_{ijlmkn} \sim i.i.d N(0, \sigma_k^2)$. The statistical tests for noninferiority (1a) ($H_0: \mu_{QIV,k} - \mu_{aQIV,k} > \log_{10}(1.5)$), and for superiority(1b) ($H_0: \mu_{QIV,k} - \mu_{aQIV,k} \geq 0$), and translating into adjusted ratios of geometric means and pertaining 2-sided CIs will be calculated based on these models.

Summary statistics will be completed by providing minimum, maximum and median titers for each vaccine group.

Analysis of binary endpoints

Statistical tests for seroconversions

The number and proportion of subjects achieving the binary endpoints (percentage of subjects with seroconversion) will be summarized by assessment (Day 22) and vaccine group, overall.

These summaries will be reported together with the associated two-sided 95% CIs for the proportion according to Clopper-Pearson.

The binary endpoints (percentage of subjects with seroconversion) will be compared between vaccine groups by the differences of proportions with two-sided 95% CI using the Miettinen and Nurminen method ([Miettinen and Nurminen 1985](#)).

Additional supportive analyses may be done using generalized linear models with a qualitative factor for vaccine group, age stratum, history of any influenza vaccination within the 3 previous seasons (yes/no), and sex. Adjusted differences and pertaining 2-sided 95% CI between vaccine groups will be calculated based on the model.

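### The primary seroconversion noninferiority intervals ignore the randomisation strata: valid, but slightly too wide if age cohort or vaccination history predicts seroconversion

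*SAP*

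**What the plan says.** SAP 4.1 randomises 1:1 with age group (50 to 59, 60 to 64) and "history of any influenza vaccination within 3 previous influenza seasons (yes/no) as stratification factors". Protocol 5.1.4 agrees. The GMT comparison is an ANCOVA containing both factors, baseline titer and sex (Protocol 8.4.2.3.3, SAP 8.1 and 11.2).

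For seroconversion, SAP 8.1 says: "The main analysis of binary immunogenicity endpoints (i.e., percentages of subjects with seroconversion) will not be adjusted for any of the covariates". SAP 11.2 says the seroconversion percentages "will be compared between vaccine groups by the differences of proportions with two-sided 95% CI using the Miettinen and Nurminen method", and Protocol 8.4.2.3.3 likewise says binary differences "will be compared using the Miettinen and Nurminen method". Neither mentions strata.

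A generalised linear model for the pooled SCR difference that includes both stratification factors is mentioned in Protocol 8.4.2.3.3, SAP 8.1 and SAP 11.2, each time as something that may or might be done.

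Results within strata are firmly planned. Protocol 8.3.7: "Primary and secondary analyses of immunogenicity and safety endpoints will be done for the total population and by age subgroup". SAP 8.5 promises that adjusted "and unadjusted immunogenicity analysis of the GMTs and SCRs will be performed by stratifying for the following subgroups", a list that includes age cohort and vaccination history. It describes the adjusted version as "same model as the main analysis by subgroup with subgroup factor removed if it is in the main model".

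**The concern.** Objective 1a passes only if all eight upper limits (four GMT ratios, four SCR differences) meet their margins. The plan uses the randomisation strata for four of these and leaves them out of the other four, without giving a reason. When allocation is balanced within strata and the strata predict the outcome, an unstratified interval counts between-stratum variation that the design has already removed. It is then wider than it need be and its true error rate falls below nominal. Only precision is at stake, and the loss falls on the sponsor: no false noninferiority claim becomes more likely.

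The subgroup results do not fill the gap, because separate results by age or history are not one pooled stratum-adjusted difference. SAP 8.5 also ties its adjusted analyses to the main model, whereas SAP 8.1 says the main SCR analysis has no covariates. For SCR, the adjusted subgroup method is therefore undefined.

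**Working it through.** **Inputs from the documents.** 1,816 evaluable, so 908 per arm; one-sided alpha 0.025; margin 10 points on QIV − aQIV; planned SCRs (QIV, aQIV) of 76%, 86% for A/H1N1, 77%, 87% for A/H3N2 and 80%, 82% for B (SAP 5, Table 3; SAP 11.2); about half the subjects in each age group (SAP 4.1).

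**Assumptions.** SCR gaps between strata, written history/age in points, additive and equal in both arms; history split 50/50 or 70/30. The documents give neither.

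**1. The plan's own figure.** For B, SE = √[(0.80×0.20 + 0.82×0.18)/908] = √(0.3076/908) = 0.01841. Power = Φ[(0.10 + 0.02)/0.01841 − 1.96] = Φ(4.56), above 99.99%. The A strains are higher still. The stated ~100% reproduces.

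**2. Size of the effect, by hand.** With a 50/50 split and gaps of 20/5, stratum rates sit ±10 and ±2.5 points from the arm mean, so each arm carries between-stratum variance 0.10² + 0.025² = 0.010625. Removing it from both arms gives 0.3076 − 0.02125 = 0.28635. The variance ratio is 0.931, and its square root 0.965. For 10/5 the ratio is (0.3076 − 0.00625)/0.3076 = 0.980, square root 0.990.

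**3. Miettinen-Nurminen score limits.** Stratified version: d = Σw_h d_h / Σw_h with Mantel-Haenszel weights w_h = n1h·n2h/(n1h + n2h), restricted maximum-likelihood variances with the N/(N−1) factor, expected counts. For B the unstratified interval is −5.62 to 1.61, width 7.228. Stratified:

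| Gaps (history/age) | History split | Width | Change |
|---|---|---|---|
| 0/0 | 50/50 | 7.234 | 0.1% wider |
| 5/2 | 50/50 | 7.218 | 0.1% narrower |
| 10/5 | 50/50 | 7.164 | 0.9% narrower |
| 20/5 | 50/50 | 6.997 | 3.2% narrower |
| 20/5 | 70/30, larger group higher | 7.029 | 2.8% narrower |
| 20/5 | 70/30, smaller group higher | 7.046 | 2.5% narrower |

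The B upper limit moves from 1.61 to 1.58 at 10/5, or to 1.49–1.52 at 20/5, against a margin of 10. At a 50/50 split, A/H1N1 goes from 7.171 to 7.105 (10/5) and 6.926 (20/5), and A/H3N2 from 7.022 to 6.954 and 6.766. The 20/5 case is extreme for the A strains: one aQIV stratum would be at 86 + 12.5 = 98.5% or 87 + 12.5 = 99.5%.

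**4. Error at the margin.** With QIV 85% and aQIV 75%, 400,000 simulated trials per scenario (Monte Carlo SE 0.00025) gave these one-sided rejection rates:

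| Gaps | Split | Unstratified | Stratified |
|---|---|---|---|
| 0/0 | – | 0.0250 | 0.0250 |
| 10/5 | – | 0.0240 | 0.0251 |
| 20/5 | 50/50 | 0.0210 | 0.0247 |
| 20/5 | 70/30, larger group higher | 0.0215 | 0.0247 |

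A separate simulation at 80% versus 70% (50/50 split) gave 0.0247, 0.0243 and 0.0218 for the unstratified interval at 0/0, 10/5 and 20/5, and 0.0175 at gaps of 30/10.

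**5. Effect on the decision.** With QIV observed at 80% and a 50/50 split, the largest QIV − aQIV difference that still passes is 6.13 points unstratified. Stratified, it is 6.13 (0/0), 6.16 (10/5) or 6.24 (20/5). If aQIV were truly 4 points worse (80% versus 76%), power would be, unstratified and stratified, 87.1% and 87.1% (0/0), 87.3% and 87.6% (10/5), 87.9% and 88.9% (20/5).

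**The case against.** The unadjusted SCR analysis is explicit, prespecified and consistent across both documents, and an ANCOVA for titers alongside an unadjusted binary comparison is not a contradiction. The interval is valid, error never exceeds nominal, and any loss is the sponsor's own. The gain rests entirely on assumed gaps: it is under 1% of width at 10/5, and about 3% needs a 20-point history effect. The plan assumes aQIV is 2 to 10 points better, so the scenarios in which power moves are not the expected ones. Replacing the primary method for four co-primary endpoints could be called disproportionate when a firm sensitivity analysis would do. SAP 8.5 could also be read as adjusted for GMTs and unadjusted for SCRs, or as pointing to the optional model in SAP 11.2.

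Most of this stands, and it is why the point is minor. It does not remove the point. The trial already randomises on these factors and uses them for the other half of the same objective. Using them here costs about 0.1% of width when they are uninformative and brings the error rate back close to nominal when they are not. That SAP 8.5 allows several readings is itself a reason to clarify it; the main point does not depend on it.

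**Conclusion.** The point holds, as a minor matter of precision. The primary SCR intervals are unstratified although randomisation is stratified, and no pooled stratum-adjusted SCR difference is firmly planned. The intervals are valid for the marginal difference. For B they are wider than necessary by about 1% at gaps of 10/5 and about 3% at 20/5, with true one-sided error of 0.024 and 0.021–0.022 in the 85% versus 75% simulation. These sizes depend on assumed gaps and an assumed history split. With no gaps there is nothing to recover. The stated ~100% SCR power, the 2,018 sample size, the 10% margin and the expected outcome of the SCR criteria at the planned rates are unchanged.

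**What to change.** Before unblinding, define the primary SCR interval as a stratified Miettinen-Nurminen difference (QIV − aQIV) over the four age-by-history strata, with prespecified Mantel-Haenszel weights and the same 10% margin. Assign strata by the rule SAP 4.1.1 already applies to the ANCOVA, where "subjects will be analyzed according to their actual age and/or influenza vaccination history". Keep the unstratified interval as a sensitivity analysis. In SAP 8.5, name the adjusted SCR method, for example the same stratified difference with the subgroup factor dropped from the strata.

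As an editorial clean-up, align the optional model's covariates: the protocol lists baseline titer but not sex, the SAP sex but not baseline titer. That model can stay optional.

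The cost is wording in SAP 8.1, 8.5 and 11.2 and Protocol 8.4.2.3.3, plus programming. Because the primary SCR method changes, an amendment with the approvals in Protocol 13.4 may be needed. If the sponsor wants to avoid that, making the stratified difference a firm sensitivity analysis would supply the missing pooled estimate, though the primary interval would stay as it is. No new data are needed. Sparse strata are unlikely: at an assumed 70/30 split the smallest has about 908 × 0.5 × 0.3 = 136 subjects per arm.
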